2.8.1.1 Adverse events of special interest / grouping of AEs

Specific groupings of adverse events of special interest will be considered and the number of patients with at least one event in each grouping will be reported. Such groups consist of adverse events for which there is a specific clinical interest in connection with deferasirox treatment. Note that certain adverse events may be reported within multiple groupings/AESIs.

AESIs are defined by MedDRA terms. Definition for retrieval (maintenance of terms considered AESI) is in a separate document in the Novartis Documentum management system at the path "CREDI Projects/I/ICL670A/Integrated Medical Safety". The MedDRA codes will be used to generate the outputs.

The AESI search table will be used to map reported adverse events to the notable adverse events groupings. The list of adverse events of special interest may be updated during the

course of the trial based on accumulating safety data. Therefore the clinical study report will list the AE groupings used and provide a listing of the corresponding AESI search table.

AESI will be summarized regardless of study drug relationship, by grouping, preferred term and treatment arm.

2.8.2 **Deaths**

Separate summaries for on-treatment and all deaths (including post-treatment deaths) will be produced by treatment arm, system organ class, and preferred term using the Safety set.

All deaths will be listed for the safety set, and post-treatment deaths will be flagged. A separate listing of deaths prior to starting treatment will be provided for all screened subjects.

2.8.3 Laboratory data

All laboratory values are generally converted into SI units and the severity grade calculated using notable and extended ranges as available in the deferasirox program standards. All values from central laboratory will be used to evaluate the primary and secondary endpoints. Any tests that are performed at local laboratories will not be used for either secondary or primary endpoints evaluation; however, collected local laboratory values will be listed along with central laboratory results and also for safety tables, all values for central and local laboratory results will be considered.

The frequency of laboratory abnormalities is displayed by parameter and treatment group. Laboratory data is summarized by presenting summary statistics of raw values and absolute and relative change from baseline.

Shift tables from baseline to highest (or lowest) post baseline value are provided for hematology: hemoglobin, WBC count, absolute neutrophils and platelets, biochemistry: alanine aminotransferase (ALT), aspartate aminotransferase (AST), serum creatinine and creatinine clearance and urinalysis: urinary total protein/creatinine ratio using normal or extended ranges. Standard oncology shift tables for laboratory parameters, based on normal ranges, are also provided.

Box plots of absolute value and the absolute change from baseline in absolute neutrophils, platelets, ALT, AST, serum creatinine, creatinine clearance and urinary total protein/creatinine ratio by time points are provided. The last available value in a time point window is used.

Criteria for clinically notable and extended laboratory ranges

Parameter	Criteria
Absolute neutrophils	<1.5×10 ⁹ /L (extended range <0.5×10 ⁹ /L)
Platelets	<100×10 ⁹ /L (extended range <50×10 ⁹ /L)
ALT/AST	>5×ULN and >2×baseline value (extended range >10×ULN and >2×baseline value)
Serum creatinine	>33% increase from baseline and >ULN at two consecutive measurements at least 7 days apart
Creatinine clearance	<60 mL/min at two consecutive measurements at least 7 days apart (extended range <40 mL/min)
Urinary total protein/creatinine ratio	>1.0 mg/mg at two consecutive measurements at least 7 days apart
Total bilirubin	>2.0 mg/dL (>34.2 umol/L)

The number and percentage of patients with laboratory results (from scheduled and unscheduled visits) meeting the criteria for notable values (see table above) will be presented.

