#### 6.7.1.3 Elevations in serum creatinine

For patients who develop an increase in serum creatinine  $\ge 33\%$  above their baseline value (the mean value established at screening Visits 1 and 2) resulting in a serum creatinine above the ULN, on two consecutive occasions, a minimum of 7 days apart, the daily dose will be reduced by 10 mg/kg (or 5 mg/kg in patients receiving 10 mg/kg).

If, after a dose reduction, serum creatinine remains above the ULN, a second dose reduction or treatment interruption is recommended. After an interruption, if serum creatinine falls below the age appropriate ULN on two consecutive visits, the investigator may resume therapy at 50% of the last dose and escalate cautiously.

Serum creatinine should be monitored weekly, preferably by local labs, for the first month after study drug initiation or dose modification. Results of these labs need to be entered into the CRF only if they are significantly abnormal, defined as at least a 33% increase over the baseline value.

If after dose reduction, a progressive increase in serum creatinine is observed, study drug may be discontinued if the investigator believes it is in the best interest of the patient. Novartis may be contacted by the investigator to discuss dosing options if the investigator so desires.

Caution should especially be used in patients with creatinine clearance between 40 and less than 60 mL/min, particularly in cases where there are additional risk factors that may impair renal function such as concomitant medications, dehydration, or severe infections.

Protocol No. CICL670A2302

Study medication should be discontinued in case serum creatinine increases >2 times the age-appropriate upper limit or if creatinine clearance <40 mL/min.

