- 8. Ocular and Audiometry examinations must be performed at screening, should a patient have evidence at the screening visit that the examination(s) were performed 6 months prior to screening then the examination(s) do not need to be repeated. The examination(s) can be performed at any time at the investigators discretion if symptomatically/clinically indicated, otherwise ocular and audiometry exams should be performed annually. The ocular and audiometry exams should be performed annually during the Evaluation Period.
- 9. Brain natriuretic peptide (BNP) blood sample should be obtained at baseline and at any time during the study when there is evidence of CHF
- 10. Serum ferritin: Two samples at screening done at least 14 days apart. If a transfusion is scheduled, draw serum ferritin PRIOR to transfusion or two weeks post-transfusion. The serum ferritin samples should be obtained in the absence of known infection.
- 11. Serum creatinine will be measured at Screening Visit 1 and Screening Visit 2 and the mean value will be used for eligibility criteria. Serum creatinine will also be measured weekly between the randomization visit and Week 4 visit. For the first month after initiation or modification of dose, labs may be obtained locally until the subject's next scheduled visit. Local labs need only be included on the eCRF in the case of a result that is a 33% increase greater than baseline result.
- 12. Creatinine clearance will be calculated by the central laboratory at every visit.
- 13. TSH and Free T4 will be measured at screening, annually and at study treatment discontinuation. TSH and Free T4 should be performed annually during the Evaluation Period.
- 14. At screening Visit 1 and 2 a urine sample (at least 15 ml) will be collected and sent to the central laboratory for urinary protein and urinary creatinine to assess the eligibility of the patient. Microscopic analysis will be performed only in case of positive dipstick. Dipsticks will be supplied by the central lab. Proteinuria (urinary protein /creatinine ratio) at Visit 1 and Visit 2 (screening) and then monthly during study.

	Screening		Randomization	Treatment Period												Week 372 a End of Treatment	8-day F	Evaluation c Period	Study Evaluation Completion	Survival d Follow-Up			
Visit	1	2	3 e	4 f	5	6	7	8	9	10	11	12	13	14	15	16	17	18-96	777	501	502, 503, etc.	778	701, 702, etc.

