## 7.5.5 Laboratory evaluations

A certified central laboratory will be utilized to process and provide results for the clinical laboratory tests summarized in Table 7-2. The central laboratory chosen for this study will provide instructions regarding the collection, processing and shipment of appropriate samples.

For first month after study drug initiation or dose modification, labs may be obtained locally until the subject's next scheduled visit. Local lab results only need to be entered on the eCRF in the event that the result demonstrates a significant change from baseline. A significant change in serum creatinine is defined as an increase of 33% greater than the baseline result. A significant change for ALT/AST/Total Bilirubin is defined as an increase of 2× the baseline value. For any other laboratory assessment, it is up to the Investigator's opinion if a laboratory result represents a significant abnormality. In the event that a local laboratory is used for assessing patient samples for trial purposes, the site/CRA must complete and submit the Novartis Local Laboratory Normal Ranges (LNR) form to the Data Manager.

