## 10.5.2.4 Analysis of laboratory data

For analyzing laboratory data, data from all sources (central and local laboratories) will be combined. Other than for weekly serum creatinine monitoring visits, central laboratory results are the only laboratory results that will be captured in the database.

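### Local creatinine results need be entered only when at least 33% above baseline, yet they are pooled with complete central data, so by-visit creatinine summaries after dose changes are biased upward

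*SAP*

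**What the plan says.** **Recording.** Protocol 6.7.1.3 asks for weekly creatinine, preferably from local laboratories, in the first month after drug start or a dose modification. On data entry it says: "Results of these labs need to be entered into the CRF only if they are significantly abnormal", with the threshold at a rise of at least 33% over baseline. Footnote 11 to Table 7-1 agrees: "Local labs need only be included on the eCRF in the case of a result that is a 33% increase greater than baseline result". Protocol 7.5.5 states the general rule: "Local lab results only need to be entered on the eCRF in the event that the result demonstrates a significant change from baseline". It adds a threshold for liver tests: "A significant change for ALT/AST/Total Bilirubin is defined as an increase of 2× the baseline value".

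**Pooling.** Protocol 10.5.2.4: "For analyzing laboratory data, data from all sources (central and local laboratories) will be combined". SAP 2.8.3 keeps local results out of the primary and secondary endpoints but adds that "also for safety tables, all values for central and local laboratory results will be considered".

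**Use.** SAP 2.8.3 plans summary statistics of raw values, absolute and relative changes from baseline, box plots by time point, highest-value or lowest-value shift tables, and counts of notable values. Notable creatinine means more than 33% above baseline and above ULN at two consecutive measurements at least 7 days apart. On the choice of value: "The last available value in a time point window is used". Neither document ranks central above local values or has a rule for selectively recorded ones.

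**The concern.** The pooled data set mixes a complete series with one filtered on its own outcome. A high local creatinine enters the database; a normal one from the same week need not. Two things follow.

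- In a window that contains a central value and later local values, the central value can be replaced by a higher one but will seldom be replaced by an ordinary one.
- The entry threshold is nearly the same as the first half of the notable-creatinine criterion. Two high values separated by an unrecorded normal value therefore appear consecutive.

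Renal dysfunction is one of the pre-specified safety concerns, so readers will look closely at these tables. Local testing follows dose changes, so the distortion falls on the patients whose dose changes most often.

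**Working it through.** The plan states no figure on this point, so there is none to reproduce. The check traces one window, then sizes the effect under stated assumptions.

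**1. One window traced.** In SAP 5.5.5 the Week 16 visit is day 112 and its window is days 99 to 126. After a dose change at that visit, weekly local tests fall on days 119, 126 and 133. The first two lie in the Week 16 window after the central value. If either is at least 33% above baseline, it becomes the last value in the window; if neither is, the central value stays. The day 133 test falls in the Week 20 window (days 127 to 154) and is superseded by the central value on day 140. In month 1, the Week 2 window is days 2 to 21, so a Week 3 local value on day 21 is last in it.

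The last-value sentence stands next to the box plots, and the SAP does not say how the tabulated means choose a value. Averaging all values in a window would also move the mean upward, since mainly high local values are added.

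**2. Consecutive-value criterion.** Assume four weekly tests, each high with probability q, independently. This ignores the further condition of exceeding ULN.

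- Truly adjacent pair: 3q²(1−q)² + 4q³(1−q) + q⁴.
- Later dose-change month (three local tests, then one central). Any two high values look adjacent, which adds 3q²(1−q)².
- Month 1. Weeks 2 and 4 are scheduled visits with creatinine recorded (Table 7-1); only Weeks 1 and 3 are extra draws. The one falsely joined pattern is high at Week 2, normal at Week 3, high at Week 4. This adds q²(1−q)².

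At q = 0.05, q²(1−q)² = 0.0025 × 0.9025 = 0.226%. The true figure is 0.677% + 0.048% + 0.001% = 0.73%. A later month gives 0.73% + 0.68% = 1.40%, and month 1 gives 0.73% + 0.23% = 0.95%.

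| q (assumed) | Truly adjacent | Flagged, later dose-change month | Flagged, month 1 |
|---|---|---|---|
| 0.05 | 0.73% | 1.40% | 0.95% |
| 0.10 | 2.80% | 5.23% | 3.61% |
| 0.20 | 10.40% | 18.08% | 12.96% |

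**3. Simulation.** Each scenario had 40,000 patients, with lognormal creatinine, baseline as the mean of two values, 13 four-weekly central visits and local tests 7, 14 and 21 days after each dose change. Assumed, not in the documents: within-patient CV 10% to 20%, true rise 0% or 15%, baseline 0.6 to 1.1 × ULN, one to six dose changes, and every normal local value left unentered.

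Mean change from baseline in dose-change windows, selective minus full recording:

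- No true change: +0.4 points at CV 10%, +3.1 at CV 15%, +6.7 at CV 20%.
- True 15% rise: +3.6 points at CV 10% to +11.3 at CV 20%.

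At CV 15% with no true change, the level is about +1.1% with central-only or full recording, against about +4.2% with selective pooling. The +1.1% comes from dividing by a noisy baseline.

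Other results at CV 15%, no true change:

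| Dose changes | Mean change, all 13 windows: full / selective | Notable creatinine: central only / full / selective |
|---|---|---|
| 1 | 1.1% / 1.4% | 3.7% / 4.5% / 5.4% |
| 3 | 1.1% / 1.8% | 3.6% / 5.6% / 7.8% |
| 6 | 1.1% / 2.5% | 3.7% / 7.1% / 11.0% |

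**4. Highest-value tables.** With six dose changes at CV 15%, the share of patients ever above ULN is 63.4% (central only), 69.0% (selective) and 72.4% (full). Leaving out normal values cannot raise a maximum; the excess over central-only reflects more testing.

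**The case against.** **Liver tests.** A reader might infer the same bias for ALT, AST and bilirubin, given the entry threshold in Protocol 7.5.5. Protocol 10.5.2.4 contradicts this: "Other than for weekly serum creatinine monitoring visits, central laboratory results are the only laboratory results that will be captured in the database". On that text there are no local liver values to pool. The notable criteria for liver tests also have no two-consecutive rule, and the ALT/AST criterion already requires more than twice baseline. This objection stands; what remains is that the two sections disagree.

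**Arms.** A reader might infer that the arms are not comparable, or that deferasirox is made to look worse. No dose-change rates are given. Creatinine-driven reductions may be commoner on deferasirox, and ferritin-driven increases may be commoner on placebo. All patients share the month 1 testing. An arm difference is plausible; its direction and size are not established.

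**Scope.** The SAP already protects the primary and secondary endpoints, including creatinine at or above 2 × ULN. Highest-value shift tables are not inflated by the omission. The pooling sentence concerns tables, so box plots may not be covered. Sites are allowed to enter normal values, and the safety outputs are descriptive. All of this stands and limits the point.

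**The remedy.** Central-only counts understate: 3.7% against 7.1% under full recording with six dose changes, an error of similar size to the overstatement at 11.0%. Weekly monitoring exists to catch rises between monthly visits. This stands too, and is why the pooled count should not be dropped.

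**Conclusion.** The point holds for serum creatinine, as a minor one. By-visit means and changes from baseline are biased upward in windows after a dose change, as are box plots if they also pool. The two-consecutive notable-creatinine count can be inflated. Creatinine clearance, if derived from local creatinine, would be biased downward.

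Under the assumptions above, the shift in an affected window runs from +0.4 to +6.7 percentage points with no true change. At CV 15%, the notable count rises from 4.5% to 5.4% with one dose change and from 7.1% to 11.0% with six. In the four-week calculation at q = 0.05, the inflation is 0.73% to 1.40% in a later dose-change month but only 0.73% to 0.95% in month 1. All of these rest on assumed variability and testing frequency, and they shrink if sites enter normal local results. The documents do not support extending the conclusion to liver tests, to worst-value shift tables, to the 2 × ULN endpoint, or to a stated bias between arms.

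**What to change.** In SAP 2.8.3:

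- Use central values only for by-visit creatinine summary statistics, changes from baseline and box plots, and say which value represents a window in the tables.
- Report the two-consecutive notable-creatinine criterion on central values, with the pooled count beside it labelled as including selectively recorded local results.
- Keep local values in listings and in worst-value tables.
- Continue to leave local values out of the 2 × ULN renal endpoint.

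Record the departure from Protocol 10.5.2.4 in SAP Section 4. Reconcile Protocol 7.5.5 with 10.5.2.4 on whether local ALT, AST and bilirubin are captured.

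The cost is SAP wording, a source filter in the laboratory programs and one extra column; no new data are needed. The downside is that central-only counts can miss rises between monthly visits, which the pooled count and the listings are kept to show.

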that the decrease in serum ferritin with deferasirox treatment is associated with a decrease in ALT indicating a possible association between reduction of iron overload and improvement in liver function (Gatterman 2010)

The serum creatinine exclusion criterion is slightly increased from >1.2 x ULN to > 1.5 ULN according to the CTCAE grade 1 which is supported by data from the US03 study.

Among patients with normal (Grade 0) creatinine at baseline (N = 149), 48 patients (32.2%) had shifts to Grade 1 and 4 patients (2.7%) had shifts to Grade 2. A total of 12 patients having a Grade 1 serum creatinine at baseline had a Grade 2 value post-baseline; this represented 54.5% of the 22 patients with a Grade 1 baseline value. Thus, the incidence of treatment emergent shifts from baseline in serum creatinine levels was 37.4% (64/171). Shifts of more than one grade occurred for just those patients with a normal baseline.

The component of the composite endpoint defining liver function impairment as reflected by ALT or AST changes is being modified in correspondence with the change in ALT/AST exclusion criterion from being > 2 x the baseline value and > 3 x ULN to > 2 x the baseline value and > 3.5 x ULN. The part of the component related to total bilirubin is left unchanged. The component of the secondary efficacy endpoint defining "time to first occurrence of serum ferritin" has been modified to correspond with the change in the serum ferritin inclusion criterion.

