For each treatment group, survival functions for time from randomization to the composite primary endpoint (event-free survival) will be estimated and displayed by the Kaplan-Meier method.

Sensitivity/supportive/exploratory analyses for the primary endpoint:

- Point estimate and two-sided confidence interval for an adjusted hazard ratio from a Cox proportional hazard regression model stratified for the randomization factors; adjustment for (partly data driven) demographic and/or baseline characteristics of clinical interest:
- Unadjusted hazard ratio estimates for each of the strata defined by the randomization factors;
- Analysis analog to the primary statistical analysis but patients with premature discontinuation of randomized study treatment will be censored at the day of last administration of randomized study treatment;
- Summary of the types of events observed;
- Statistical analyses based on the PPS instead of the FAS.

Statistical analysis methods for secondary efficacy endpoints:

Analyses will be described in the full clinical study protocol.

Statistical analysis methods for safety endpoints:

Following (Fleming 2008), the goal of this exploratory trial is not to determine whether there is significant evidence to rule out the null hypothesis of no increased risk.

In contrast, the objective here is to exclude levels of increased risk (for pre-specified adverse events mentioned in the Endpoints section) that would be clinically unacceptable in the context of the level of benefit that is likely to be provided by iron chelation using deferasirox in MDS patients with iron overload. Therefore, two-sided 95% confidence intervals for risk (or hazard, if applicable) ratios will be calculated. Incidences of treatment emergent (serious) adverse events (including combinations of MedDRA terms as defined by Standardized MedDRA Queries) will be summarized by treatment group. Laboratory data will be summarized using descriptive statistics and shift tables (using CTCAE classification where available) by treatment group.

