#### **Grading of laboratory data**

For laboratory tests covered by the Common Terminology Criteria for Adverse Events (CTCAE) version 3.0 NCI 2006, the study's biometrics team will grade laboratory data accordingly with the exception of grade 5 (death). For laboratory tests covered by CTCAE, a grade 0 will be assigned for all non-missing values not graded as 1 or higher. For laboratory tests where grades are not defined by CTCAE, results will be graded by the low/normal/high classification based on laboratory normal ranges.

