#### Reporting of laboratory data

The following by-treatment summaries will be generated separately for hematology, biochemistry and urinary laboratory tests:

- Frequency table for newly occurring on-treatment grades 3 or 4.
- Shift tables using CTCAE grades to compare baseline to the worst on-treatment value.
- For laboratory tests where CTCAE grades are not defined, shift tables using the low/normal/high/(low and high) classification to compare baseline to the worst ontreatment value.

For a specific laboratory test, patients with newly occurring on-treatment grade 3 or 4 are defined as:

- Patients with baseline grade missing, 0, 1 or 2 and worst on-treatment grade 3 or 4 (percentage to be based on all patients with baseline grade missing, 0, 1 or 2).
- Patients with baseline grade missing, 0, 1, 2 or 3 and worst on-treatment grade 4 (percentage to be based on all patients with baseline grade missing, 0, 1, 2 or 3).

The following listings will be generated:

- Listing of laboratory data for patients with newly occurring grade 3 or 4 laboratory toxicities.
- Listing of laboratory data for patients with values outside the laboratory normal ranges with values flagged to show the corresponding CTCAE grades and the classifications relative to the laboratory normal ranges.
- Listing of all laboratory data with values flagged to show the corresponding CTCAE grades and the classifications relative to the laboratory normal ranges.

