5.3 Laboratory parameters derivations

Grade categorization of lab values will be assigned programmatically as per NCI Common Terminology Criteria for Adverse Events (CTCAE) version 4.03 or later. The calculation of laboratory CTC grades will be based on the observed laboratory values only; clinical assessments will not be taken into account.

For laboratory tests where grades are not defined by CTCAE 4.03 or latest version, results will be graded by the low/normal/high (or other project-specific ranges, if more suitable) based on laboratory normal ranges.

A severity grade of 0 will be assigned for all non-missing lab values not graded as 1 or higher. Grade 5 is not applicable. For laboratory tests that are graded for both low and high values, summaries will be done separately and labelled by direction, e.g., sodium will be summarized as hyponatremia and hypernatremia.

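### SAP 2.8.3 omits, undeclared, the CTCAE shift tables and newly occurring grade 3/4 laboratory tables required by protocol 10.5.2.4, and its other outputs only partly compensate

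*SAP*

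**What the plan says.** Protocol 10.5.2.4, under its reporting heading, sets by-treatment summaries for hematology, biochemistry and urinary tests. Two use CTCAE grades: "Frequency table for newly occurring on-treatment grades 3 or 4" and "Shift tables using CTCAE grades to compare baseline to the worst on-treatment value". Newly occurring grade 3 or 4 is counted among patients with baseline grade missing or 0 to 2, and newly occurring grade 4 among those with baseline grade missing or 0 to 3. Low/normal/high shifts are kept for tests that CTCAE does not grade. The synopsis makes the same commitment for safety: "shift tables (using CTCAE classification where available) by treatment group". The grading version is "Common Terminology Criteria for Adverse Events (CTCAE) version 3.0".

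SAP 2.8.3 describes a different scheme, with "the severity grade calculated using notable and extended ranges as available in the deferasirox program standards". Nine parameters (hemoglobin, WBC, neutrophils, platelets, ALT, AST, creatinine, creatinine clearance, urinary protein/creatinine ratio) get shift tables on normal or extended ranges. Then: "Standard oncology shift tables for laboratory parameters, based on normal ranges, are also provided". The section also gives change from baseline, box plots for seven of the nine parameters, and counts of patients with notable values.

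SAP 5.3 still assigns grades "as per NCI Common Terminology Criteria for Adverse Events (CTCAE) version 4.03 or later" and mentions separate summaries by direction for tests graded both ways, but names no table. SAP section 4 lists one change to the protocol's analyses, the redefinition of newly occurring neutropenia and thrombocytopenia.

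**The concern.** Other laboratory abnormalities are part of a secondary safety endpoint, and raised creatinine is a known effect of the drug. The trial admits patients with abnormal values: creatinine up to 1.5×ULN, ALT/AST up to 3.5×ULN, bilirubin up to 1.5×ULN. A low/normal/high shift table cannot separate mild from severe abnormality, and it places a patient who starts high and goes higher in the same cell as one who stays put. A graded shift table separates them when a grade boundary is crossed, and the protocol's denominators stop patients already at a severe grade from being counted as new cases.

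Laboratory tables also matter more than usual here. SAP 2.8.1 does not grade adverse events by CTCAE, and protocol 7.5.1 keeps laboratory changes outside its stated criteria off the adverse event form. SAP section 1 says the study report will be written from this plan, so a table not named in it may not be produced.

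**Working it through.** **1. Text comparison.** Protocol 10.5.2.4 requires a CTCAE shift table and a newly occurring grade 3/4 table. SAP 2.8.3 names neither, SAP 5.3 derives the grades without a destination, and SAP section 4 is silent on both the tables and the CTCAE version. The omission is a matter of text.

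**2. Creatinine.** Inputs: the notable criterion is a rise above 33% and a value above ULN, confirmed at least 7 days later (SAP 2.8.3); the renal endpoint is at least 2×ULN, confirmed (SAP 2.8); entry is allowed up to 1.5×ULN (protocol 5.2); no extended range is listed. Take grade 1 as ending at 1.5×ULN, as the Amendment 3 rationale implies.
- A patient with baseline b can pass 1.5×ULN without being notable if 1.5 < 1.33 × b, that is b > 1.5/1.33 = 1.13×ULN.
- Example: 1.4 to 1.8×ULN is 1.8/1.4 − 1 = 28.6%. It is not notable, it is below 2×ULN, and it is high-to-high.
- Counter-check: 1.5 to 2.0×ULN is 33.3%. If confirmed, it meets both criteria.

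The gap is therefore rises of 33% or less from a baseline above about 1.13×ULN, plus unconfirmed rises. The CTCAE shift table would show a move from grade 1 to grade 2; the grade 3/4 table would not.

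**3. ALT/AST.** Notable means above 5×ULN and above 2×baseline; extended means above 10×ULN and above 2×baseline. The notable threshold is max(5, 2b):
- b = 2×ULN: notable above 5×ULN.
- b = 3.5×ULN: notable above 7×ULN.
- Both: extended above 10×ULN.

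Large rises from an abnormal baseline are counted. Smaller ones are not counted as notable.

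**4. Other tests.**
- Total bilirubin: one fixed cut-off (2.0 mg/dL), not among the nine shift parameters, no box plot.
- WBC: in the shift list, but with no notable or extended range given. Hemoglobin is the same, partly covered by the anemia analysis in SAP 2.8.
- Remaining chemistry (GGT, alkaline phosphatase, electrolytes): no extended range and no baseline-relative criterion.
- Neutrophils and platelets: notable below 1.5 and below 100 ×10⁹/L, with no baseline condition. The IPSS cytopenia limits in SAP 5.3.2 are 1.8 and 100, so patients already low at entry can count as notable in either arm. SAP 2.8 counts newly occurring cases only at 1.0 and 50. The value 1.0 matches neither the notable (1.5) nor the extended (0.5) neutrophil cut-off, although section 4 says the notable definition is used.

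**5. Illustration from data the protocol quotes.** In the Amendment 3 creatinine data, 48 + 4 + 12 = 64 shifts and 64/171 = 37.4%, which reproduces the stated figure. Of the 12 moves from grade 1 to grade 2, "this represented 54.5% of the 22 patients with a Grade 1 baseline value". In a table with only normal and high, those 12 would be high-to-high: 12/64 = 19% of all shifts and 12/(4 + 12) = 75% of shifts to grade 2.

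In the pooled ALT table, (38 + 1 + 1)/71 = 56% had baseline ALT above ULN. Of those 40, 18 ended above ULN: 1 worse by a band, 15 unchanged, 2 better. The other 22 returned to normal.

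**The case against.** The strongest case against is that the SAP offers much more than normal-range shifts. The sentence on those tables says they come in addition to nine-parameter shifts that may use extended ranges, and extended cut-offs are listed for ALT/AST, neutrophils, platelets and creatinine clearance. Change from baseline is summarized in absolute and relative terms, the ALT/AST and creatinine notable criteria are relative to baseline, and SAP 2.8 adds the confirmed 2×ULN renal endpoint, newly occurring cytopenias and anemia. SAP 5.3 keeps CTCAE grading, SAP 2.1 points to protocol section 10, and the layout of the standard oncology tables lies in material not available here. The trial is also not confirmatory.

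Most of this stands. A reader might infer that the SAP has replaced graded tables with normal-range tables, so that worsening from an abnormal baseline is invisible. The documents do not support that: several outputs show part of it, and grading has not been abandoned.

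A reader might also take 19%, 75% or 56% as the share of worsening that this SAP would hide. They are not. They describe a pure normal-range table applied to other studies' data, and only 1 of the 40 patients with raised baseline ALT worsened by a band.

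The objection does not remove the omission. SAP 2.1 follows protocol section 10 only as the SAP details it, and SAP 2.8.3 details something else. Summary statistics do not count patients, and the box plots use the last value in a window, not the worst.

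**Conclusion.** The point holds as an undeclared and only partly compensated omission. The SAP states a different and coarser categorical method than the protocol for laboratory abnormalities, leaves its own CTCAE grades without a table, and opens the CTCAE version. The gaps are creatinine rises of 33% or less from a baseline above about 1.13×ULN, total bilirubin, WBC and the other chemistry tests, together with neutrophil and platelet notable counts that ignore baseline.

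This rests on three assumptions: creatinine grade 1 ends at 1.5×ULN; the ranges listed in SAP 2.8.3 are the ones that apply, since the program standards it cites are not in the documents; and the standard oncology shift tables use only low, normal and high categories. The number of patients affected cannot be estimated from the documents. Because a secondary safety endpoint is involved and the grades are already derived, the change should be made.

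**What to change.** In SAP 2.8.3, state that the CTCAE grades from 5.3 feed two by-arm outputs: shift tables from baseline to worst on-treatment grade, and tables of newly occurring grade 3/4 and of newly occurring grade 4 with the denominators of protocol 10.5.2.4. Rely on normal-range shifts alone only for tests without CTCAE grades. Name one CTCAE version and, if it is not 3.0, declare that in SAP section 4. Keep the notable and extended-range outputs as additions. If the sponsor prefers not to produce the protocol tables, section 4 should say so and give the reason.

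The cost is SAP wording and a few more standard tables. No new data or derivations are needed beyond settling the version.
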